## **1. INTRODUCTION**

The following Statistical Analysis Plan (SAP) provides the outline for the statistical analysis of the data from AROHBV1001 study.

This Statistical Analysis Plan (SAP) is an adjunct to the Arrowhead Pharmaceuticals protocol number AROHBV1001 (Version 6.0, 28 February 2020). The planned analyses identified in this SAP may be included in clinical study reports (CSRs), regulatory submissions, or future manuscripts. Also, post hoc analyses not necessarily identified in this SAP may be performed to further examine study data. Any post hoc, or unplanned, exploratory analyses performed will be clearly identified as such in the final CSR.

## 2. PROJECT OVERVIEW

### 2.1 Study Design

This is a phase 1/2a single dose-escalating study to evaluate the safety, tolerability and pharmacokinetic effects of ARO-HBV in Normal Healthy Volunteers (NHV) and multiple escalating doses to evaluate safety, tolerability and pharmacodynamic effects in HBV patients. ARO-HBV is a drug candidate developed by Arrowhead Pharmaceuticals, Inc. to treat chronic HBV infection. ARO-HBV is administered through subcutaneous injection.

This study will include the following cohorts, with the dose escalation schedule plotted as below. Dose escalation and start of new cohort are subject to Data Safety Committee (DSC) approval based on the evaluation of all available safety data.

- Normal Healthy Volunteers (NHV): Cohorts 1, 2, 3, 4 and 5.

Each NHV cohort will recruit 6 healthy volunteers, with subjects randomized to receive placebo (2 subjects) or active ARO-HBV (4 subjects) in a double blinded fashion. The first two subjects in each cohort serve as sentinel participants (one ARO-HBV and one placebo). NHV cohorts will be single dosed as follows:

- Cohort 1: 35 mg ARO-HBV, at Day 1
- Cohort 2: 100 mg ARO-HBV, at Day 1
- Cohort 3: 200 mg ARO-HBV, at Day 1
- Cohort 4: 300 mg ARO-HBV, at Day 1
- Cohort 5: 400 mg ARO-HBV, at Day 1

- Chronic Hepatitis B (CHB) Patients: Cohorts 1b, 1c, 2b, 3b, 4b, 5b, 6, 7, 8, 9, 10, 11 and 12.

CHB cohorts 1b, 1c, 2b, 3b, 4b and 5b will each enroll a minimum of 4 and a maximum of 8 subjects and the remaining CHB cohorts (except Cohort 12) will each recruit a maximum of 4 chronic hepatitis B patients, with all subjects receiving three doses of ARO-HBV at dose intervals ranging from once every week to once every 4 weeks in an open label fashion. All CHB cohorts except Cohorts 8 and 9 will include CHB patients regardless of NUC or HBeAg status. Cohort 8 will include HBeAg(+) and treatment naïve patients, and Cohort 9 will include HBeAg(+) and entecavir or tenofovir experienced patients. CHB patients on current nucleos(t)ide (NUC) therapy (entecavir or tenofovir) will stay on NUC therapy for the study duration. CHB patients not on NUC therapy (NUC naïve) will be started on either entecavir or tenofovir (selection between entecavir and tenofovir based on site Principal Investigator (PI) discretion) on Day 1. Cohort 12 will enroll 12 CHB patients who will either enter the study on NUCs or start NUCs on Day 1. Cohort 12 patients will also initiate daily JNJ-56136379 (JNJ-6379) 250 mg on Day 1 and continue through Day 84.

CHB cohorts will be multi-dosed as follows:

- Cohort 1b: 25 mg ARO-HBV, at Days 1, 29 and 57
- Cohort 1c: 50 mg ARO-HBV, at Days 1, 29 and 57
- Cohort 2b: 100 mg ARO-HBV, at Days 1, 29 and 57

- Cohort 3b: 200 mg ARO-HBV, at Days 1, 29 and 57
- Cohort 4b: 300 mg ARO-HBV, at Days 1, 29 and 57
- Cohort 5b: 400 mg ARO-HBV, at Days 1, 29 and 57
- Cohort 6: 100 mg ARO-HBV, at Days 1, 15 and 29
- Cohort 7: 100 mg ARO-HBV, at Days 1, 8 and 15
- Cohort 8 (HBeAg +, Treatment naïve): 300 mg ARO-HBV, at Days 1, 29 and 57
- Cohort 9 (HBeAg +, NUC (entecavir/tenofovir) experienced): 300 mg ARO-HBV, at Days 1, 29 and 57
- Cohort 10: 200 mg ARO-HBV, at Days 1, 8 and 15
- Cohort 11: 300 mg ARO-HBV, at Days 1, 8 and 15
- Cohort 12: 200 mg ARO-HBV, at Days 1, 29 and 57 + 250 mg daily JNJ-6379 + NUCs

**Dose Escalation Schedule**

Healthy Volunteers (double blind) *			CHB Patients (open label)	
Cohort	Dose (Day 1)	Day 8 safety evaluation	Cohort	Dose Regimen
Cohort 1	35 mg		Cohort 1b (all eligible CHB patients regardless of NUC or HBeAg status)	ARO-HBV 25 mg dosed on Day 1, 29, 57
			Cohort 1c (all eligible CHB patients regardless of NUC or HBeAg status)	ARO-HBV 50 mg dosed on Day 1, 29, 57
Cohort 2	100 mg		Cohort 2b (all eligible CHB patients regardless of NUC or HBeAg status)	ARO-HBV 100 mg dosed on Day 1, 29, 57
Cohort 3	200 mg		Cohort 3b (all eligible CHB patients regardless of NUC or HBeAg status)	ARO-HBV 200 mg dosed on Day 1, 29, 57
Cohort 4	300 mg		Cohort 4b (all eligible CHB patients regardless of NUC or HBeAg status)	ARO-HBV 300 mg dosed on Day 1, 29, 57
Cohort 5	400 mg		Cohort 5b (all eligible CHB patients regardless of NUC or HBeAg status)	ARO-HBV 400 mg dosed on Day 1, 29, 57
			Cohort 6 (all eligible CHB patients regardless of NUC or HBeAg status)	ARO-HBV 100 mg dosed on Day 1, 15, 29

		→	Cohort 7 (all eligible CHB patients regardless of NUC or HBeAg status)	ARO-HBV 100 mg dosed on Day 1, 8, 15
		→	Cohort 8 HBeAg+, treatment naïve	ARO-HBV 300 mg dosed on Day 1, 29, 57
		→	Cohort 9 HBeAg+, entecavir or tenofovir experienced	ARO-HBV 300 mg dosed on Day 1, 29, 57
		→	Cohort 10 (all eligible CHB patients regardless of NUC or HBeAg status)	ARO-HBV 200 mg dosed on Day 1, 8, 15
		→	Cohort 11 (all eligible CHB patients regardless of NUC or HBeAg status)	ARO-HBV 300 mg dosed on Day 1, 8, 15
		→	Cohort 12 (all eligible CHB patients regardless of NUC or HBeAg status)	JNJ-6379 daily 250mg + ARO-HBV 200 mg dosed on Day 1, 29, 57

\* All NHV Cohorts use 2 sentinel subjects

NHV cohorts will be followed for a maximum of 13 weeks from the beginning of the screening to the Day 29 EOS examination. CHB cohorts will be followed for approximately 25 weeks from screening to the Day 113 EOS examination. During the study period, safety assessments, immunologic assessments (CHB cohorts in New Zealand only), HBV virology assessments (CHB cohorts), Immunogenicity (CHB cohorts), pharmacodynamics endpoints (NHV cohorts), cytokines, complement (NHV cohorts), excretion and metabolism will be conducted as per the Schedule of Assessments in the protocol. CHB patients consenting to participate in the additional follow-up period will be followed as per Additional Follow-Up Schedule of Assessments (refer to the study protocol), every 56 days ( $\pm$  5 days) for 5 additional visits after Day 113. In addition, Cohort 12 patients will require follow-up until the Day 337 ( $\pm$  5 days).

Pharmacokinetic (PK) intensive sampling will be conducted for NHV cohorts on Day 1 (dosing day) at the time of 0 (pre-dose), 15 minutes, 0.5, 1, 2, 3, 6, 24 and 48 hours post-dose. No PK data will be sampled for CHB cohorts, except in Cohort 12 where plasma will be collected two-hours post-ARO\_HBV dose to measure plasma concentration of ARO-HBV, JNJ-6379, and NUC (ETV or TDF).

## **2.2 Objectives**

### **2.2.1 Primary objective**

- To determine the incidence and frequency of adverse events possibly or probably related to treatment as a measure of the safety and tolerability of ARO-HBV using escalating single doses in healthy volunteers (NHV) and escalating multiple doses in patients chronically infected with hepatitis B virus (CHB).

### **2.2.2 Secondary objective(s)**

- To evaluate the single-dose pharmacokinetics of ARO-HBV in healthy volunteers
- To determine the reduction from Day 1 pre-dose baseline to post-dose nadir of HBsAg in response to ARO-HBV in CHB patients as a measure of activity

### **2.2.3 Exploratory objective**

- To determine the reduction from Day 1 pre-dose baseline to post-dose nadir of HBcrAg, HBsAg, HBV DNA, HBV RNA (if scientifically feasible) and HBeAg (e+ only), in response to ARO-HBV (alone or in combination with JNJ-6379) in CHB patients as a measure of activity. The following categories will be considered for HBV DNA: >LLQ, <LLQ target detected and <LLQ target not detected.
- To evaluate the effect of single doses of ARO-HBV on cytokines (Cytokine panel A: interleukin-6 [IL-6], monocyte chemoattractant protein-1 [MCP-1], tumor necrosis factor-alpha [TNF-alpha], interleukin-8 [IL-8], interleukin-1beta [IL-1beta], interferon alpha [IFN-alpha], IL-10, IL-12 [p40], IL-12 [p70], macrophage inflammatory protein-1alpha [Mip-1alpha]) in healthy volunteers.
- To evaluate the effect of single escalating doses of ARO-HBV on complement factors Bb, CH50, C5a, C4a, and C3a in healthy volunteers.
- To collect plasma samples in healthy volunteers for subsequent metabolite identification (reported in a separate report outside of this study)
- To collect urine samples in healthy volunteers for subsequent determination of urinary excretion and metabolite identification (reported in a separate report outside of this study)
- To evaluate the effect of multiple doses of ARO-HBV (alone or in combination with JNJ-6379) on cytokines (Cytokine panel B: TNF-alpha, IFN-gamma, CXCL-9, and CXCL-10) in CHB patients
- To evaluate the effect of multiple doses of ARO-HBV (alone or in combination with JNJ-6379) on HBV patient immune cell profile including T-cells, NK cells, B cells and monocytes (if scientifically feasible)
- To evaluate the effect of multiple doses of ARO-HBV (alone or in combination with JNJ-6379) on HBV antigen specific T-cell response (if scientifically feasible).
- To evaluate the effect of interferon response gene single nucleotide polymorphisms (SNPs) including IL28B on response to ARO-HBV (alone or in combination with JNJ-6379).

- To determine the incidence and frequency of adverse events possibly or probably related to treatment as a measure of the safety and tolerability of ARO-HBV in combination with JNJ-6379 in patients chronically infected with hepatitis B virus (CHB) (Cohort 12 only).
- To determine plasma concentration of ARO-HBV, JNJ-6379, and NUCs at specified timepoints in HBV patients (Cohort 12 only).

## 2.3 Study Endpoints

### Safety endpoints

- Monitoring of AEs/SAEs
- Physical examinations
- Vital signs
- ECG measurements
- Injection Site Reactions (Mild, Moderate or Severe)
- Clinical laboratory tests (hematology, biochemistry, coagulation, urinalysis)
- Concomitant medications/therapy, and
- Reasons for treatment discontinuation due to toxicity

### Cellular Immunologic Endpoints (CHB Cohorts in New Zealand only)

- Patient immune cell profile: T cell subsets (activation and exhaustion state), NK cell subsets (activation and exhaustion state), B cell subset, monocyte subsets. To be conducted if scientifically feasible.
- HBV antigen specific T cell response (including HBcAg, HBsAg). To be conducted if scientifically feasible.

### Virology Endpoints (CHB Cohorts only)

- Qualitative assessments: HBsAg, HBeAg, anti-HBsAg, anti-HBeAg
- Quantitative assessments: HBV DNA, qHBsAg, qHBeAg, qHBcrAg, qHBV RNA (if feasible), anti-HBsAg and ratio of bound/free anti-HBsAg
- HBV genotyping and HBV sequencing

### Immunogenicity (CHB Cohorts only)

- Anti-drug antibodies

### Pharmacokinetics (NHV Cohorts and limited PK in Cohort 12)

- Plasma PK blood samples will be collected at Day 1
- Plasma concentrations of ARO-HBV, NUC and JNJ-6379 will be measured at a single post-dose time point in Cohort 12 only

### Cytokines

- Cytokine panel A (NHV Cohorts): interleukin-6 [IL-6], monocyte chemoattractant protein-1 [MCP-1], tumor necrosis factor-alpha [TNF-alpha], interleukin-8 [IL-8], interleukin-1beta [IL-1beta], interferon alpha [IFN alpha], IL-10, IL-12 [p40], IL-12 [p70], macrophage inflammatory protein-1alpha [Mip-1alpha]
- Cytokine panel B (CHB Cohorts): TNF-alpha, IFN gamma, CXCL-9, and CXCL-10

### Complement (NHV Cohorts)

- Bb, CH50, C5a, C4a, and C3a

### Genetic Testing (consenting CHB patients only)

- Interferon response gene SNP analysis testing

### Excretion and Metabolism Parameters

- Samples for metabolic analyses will be stored and reported outside of this study
- Urine collections will be collected per the Schedule of Assessments.

## **2.4 Sample Size**

No formal statistical calculation of sample size will be used for this Phase 1/2a study. The sample size is empirical. The small numbers per cohort in this study are not intended for statistical hypothesis inference analysis. Results from this study will be utilized in sample size calculations for subsequent studies.

This study will involve approximately 30 eligible normal healthy volunteers in NHV cohorts and a minimum of 60 and a maximum of 84 CHB patients in CHB cohorts. Each of the 5 NHV cohorts will recruit 6 healthy volunteers. CHB cohorts 1b, 1c, 2b, 3b, 4b and 5b will recruit a minimum of 4 and a maximum of 8 patients, and CHB cohorts 6, 7, 8, 9, 10, 11 will recruit a maximum of 4 CHB patients. Cohort 12 will recruit 12 CHB patients.

## **2.5 Randomisation**

### NHV Cohorts

The six (6) healthy volunteers in each of the five (5) NHV cohorts will be randomized at a ratio of 2:1 (active: placebo) to receive ARO-HBV or Placebo in a double-blind fashion. Therefore 4 subjects will be randomized to receive ARO-HBV and 2 subjects to receive placebo in each of the NHV cohorts.

### CHB Cohorts

All CHB patients in each of the 13 CHB cohorts will receive ARO-HBV (alone or in combination with JNJ-6379) and daily NUC, and no randomization is applied.

### 3. STATISTICAL CONSIDERATIONS

Data will be handled and processed according to the sponsor's representative (Novotech (Australia) Pty Ltd) Standard Operating Procedures (SOPs), which are written based on the principles of GCP.

All data collected on the eCRFs will be presented in the data listings and will be listed and sorted by subject number and visit, where applicable. All summaries will present the data by ARO-HBV dose level/cohort and overall (total subjects), as applicable.

Data collected during the main study (up to the Day 29 or Day 113 EOS visits) and at the additional follow-up visits (CHB cohorts only) will be presented in the same summary table, as appropriate. The first part of each table will present the main study results for the specific analysis. The second part of each table will include all data collected during the study, including data collected during the follow-up period, for the subset of CHB patients that consented to participate in the follow-up. All data will be included in the listings, and data collected during the follow-up period will be flagged in all event/medication-based listings. Separate figures that include all data will be presented for the subset of patients that participated in the follow-up period.

Unless otherwise stated, the following statistical approaches will be taken:

- Continuous variables: Descriptive statistics will include the number of non-missing values (N), mean, standard deviation (SD), median, minimum, maximum.
- Categorical variables: Descriptive statistics will include frequency counts and percentages per category. Percentages will be rounded to one decimal place, with the denominator being the number of subjects in the relevant population with non-missing data, unless otherwise specified.
- Imputation: No missing data will be imputed generally.
- Confidence intervals (CIs): CIs will be two-sided and will use 95% confidence levels unless specified otherwise.
- Baseline: Baseline values will be defined as the last non-missing observation (pre-dose value closest to the first dose) for each subject prior to the dosing of study medication (i.e. start of injection on Day 1).
- Repeat assessments (Safety): If there is a repeat test, the repeat result will be used in the analysis table and the original result will only be listed in the data listing.
- Repeat assessments (Virology): Certain virologic assessments such as qHBsAg may be batch analyzed per patient at the end of study. In cases where both batch-analyzed and non-batch analyzed data are available, batch analyzed data will be used in the analysis table and all other results will be listed. In other instances, repeat tests may have been performed for other reasons than batch-analysis. If there is a repeat test, the repeat result will be used in the analysis table and the original result will only be listed in the data listing.

Continuous safety variables will be reported to the same precision as the source data. Derived variables will be reported using the same precision to the value(s) from which they were derived. For the reporting of descriptive statistics, the mean (95% CI) and median will be reported to 1 decimal place more than the source data; the minimum, and the maximum values will be presented to the same precision as the source data; and standard deviation will be

reported to 2 decimal places more than the source data. Rounding is not allowed in the middle of the calculation. It only takes place at the last step to report the final result. Post-dose time points/visits will be calculated relative to start time of injection on Day 1. Study day will be defined as assessment date minus dosing day +1.

The NHV cohorts (Cohorts 1, 2, 3, 4, and 5) will be summarized separately from the CHB cohorts (Cohorts 1b, 1c, 2b, 3b, 4b, 5b, 6, 7, 8, 9, 10,11 and 12). The dose levels (cohorts) will be referred to in the text, tables and listings as follows.

NHV Cohorts:

- Coh1: ARO-HBV (35 mg)
- Coh2: ARO-HBV (100 mg)
- Coh3: ARO-HBV (200 mg)
- Coh4: ARO-HBV (300 mg)
- Coh5: ARO-HBV (400 mg)
- Combined ARO-HBV
- Combined Placebo
- Total (including all ARO-HBV and Placebo)

CHB Cohorts:

- Coh1b: ARO-HBV (25 mg, Q28D)
- Coh1c: ARO-HBV (50 mg, Q28D)
- Coh2b: ARO-HBV (100 mg, Q28D)
- Coh3b: ARO-HBV (200 mg, Q28D)
- Coh4b: ARO-HBV (300 mg, Q28D)
- Coh5b: ARO-HBV (400 mg, Q28D)
- Coh6: ARO-HBV (100 mg, Q14D)
- Coh7: ARO-HBV (100 mg, Q7D)
- Coh8: ARO-HBV (300 mg, Q28D, HBeAg+/Trt Naive)
- Coh9: ARO-HBV (300 mg, Q28D, HBeAg+/NUC)
- Coh10: ARO-HBV (200 mg, Q7D)
- Coh11: ARO-HBV (300 mg, Q7D)
- Coh12: ARO-HBV (200 mg, Q28D) + JNJ-6379 250mg
- Combined ARO-HBV
- Pooled ARO-HBV (300 mg, Q28D)

where Q7D: dosing once every 7 days,  
Q14D: dosing once every 14 days,  
Q28D: dosing once every 28 days

Summary tables and listings will be produced separately for NHV cohorts (Cohorts 1, 2, 3, 4 and 5) and CHB cohorts (Cohorts 1b, 1c, 2b, 3b, 4b, 5b, 6, 7, 8, 9, 10,11 and 12). The Pooled ARO-HBV (300 mg, Q28D) group will only be presented for the safety outputs.

Due to the large number of treatment columns that will be displayed in the outputs, the results for a specific parameter/visit could span multiple pages. Summaries will be presented by groups of treatments, i.e., if only CHB Coh1b to Coh7 can be fit onto a page, all of the results for these cohorts will be presented on the subsequent pages before the results for the initial visits of the next group of cohorts are presented. Where appropriate, the outputs may also be

transposed to present the treatment information in rows instead of columns to facilitate the review process.

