Blood samples will be collected from each NHV (Cohorts 1-5) participant during the study for Complement analysis after dose 1 (all cohorts). Two blood samples will be collected at each collection time. One sample will be processed to produce serum for complement CH50 analysis, and one sample will be processed to produce plasma, which will be analyzed to determine the level of split products Bb, C5a, C4a, and C3a. Initially the 0 (pre-) and 2-hour post-dose samples will be analyzed, with the remaining samples analyzed only if a change from pre-dose baseline is observed at 2 hours.

Excretion and Metabolism:

Seven blood samples will be collected from each subject for metabolic analysis after dose 1 (Cohorts 2-5) per the Schedule of Assessments. Samples will be frozen at -80°C for analysis outside of this study.

Urine collections will be performed after dosing per the Schedule of Assessments.

Data Analysis:

Two separate data analyses will be performed, one for all subjects through EOS (Day 29 for NHVs and Day 113 for CHB patients), and one additional and separate analysis for CHB patients who consent to the additional follow up through Day 337 (Cohort 12 only) or Day 393. Separate analyses including and excluding Cohort 12 may also be completed.

Screening, Compliance, Tolerability and Safety Data:

In general, safety analyses will be performed and the results summarized by cohort. Post-treatment safety assessments will be compared with measurements recorded at baseline. Treatment emergent AEs will be summarized using the latest version of the Medical Dictionary for Regulatory Activities (MedDRA) by System Organ Class (SOC) and Preferred Term (PT). The incidence and frequency of AEs, SAEs, related AEs, related SAEs, and AEs leading to discontinuation, will be summarized by cohort per SOC, PT, and severity. All Adverse Events will also be presented in listings. The duration of AEs will be determined and included in listings, along with the action taken and outcome. The incidence of laboratory abnormalities will be assessed using descriptive summary statistics and shift tables. Vital sign measurements will be summarized at each scheduled time point using descriptive statistics. Abnormal physical examination findings will be summarized by time point and presented in subject listings. ECG parameters, changes from baseline, and qualitative assessments will be summarized. Pregnancy and FSH test results will be listed separately by time point.

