Cohort 12 uses a combination of NUCs + ARO-HBV + JNJ-6379. Throughout the study all patients have been treated with the combination of NUCs + ARO-HBV. It is thought that by using an siRNA approach to silence production of viral antigen in combination with NUCs to inhibit viral replication and JNJ-6379 which inhibits capsid assembly and cccDNA formation the response to treatment and potentially the rate of functional cure could be enhanced. ARO-HBV + NUCs has been well tolerated throughout the AROHBV1001 study. JNJ-6379 in combination with NUCs has also been well tolerated in CHB clinical studies. In vitro, JNJ-6379 does not inhibit phosphorylation of tenofovir or entecavir. It is not expected that JNJ-6379 and ARO-HBV will have overlapping or additive toxicity. As such, the benefit of this combination “triple” therapy is expected to outweigh risk of toxicity.

6.3 *Criteria for Dose-escalation and Stopping Rules*

Escalation to the next cohort will proceed according to the study design until the 400 mg dose level and all subsequent cohorts are completed unless the trial is stopped early by the Data Safety Committee (DSC) or Sponsor. Dose escalation will require approval by the DSC based on all cumulative available safety data through Day 8 of the current cohort. Dose escalation will proceed until all cohorts are fully enrolled or until the study is stopped or the DSC votes to not escalate to the next dose.

A decision to stop the trial early or discontinue drug in an individual subject or group of subjects **may** (following a case-by-case decision based on consultation between the sponsor, DSC and the PI) be indicated based on any of the following:

1. A single Serious Adverse Event(SAE) (defined in Section 9.1) considered at least possibly related to ARO-HBV and/or JNJ-6379
2. One of the following abnormal results at least possibly related to ARO-HBV and/or JNJ-6379:
 - In NHVs, treatment emergent ALT or AST > 3X ULN which must be confirmed by repeat blood draw within 48 hours of initial results.
 - In CHB patients, treatment emergent ALT or AST > 3X Day 1 pre-dose baseline confirmed by repeat blood draw within 48 hours of initial results **AND** ALT > 10X ULN **AND** any one of the following:
 - Total Bilirubin newly elevated to 2X ULN AND 2X Day-1 pre-dose baseline (confirmed on repeat lab draw within 48 hours) or
 - Decrease in serum albumin of 0.5 g/dL or greater (confirmed on repeat lab draw within 48 hours)

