 - Treatment emergent platelet count < 70,000 per microliter in NHVs or < 50,000 in CHB patients, confirmed on repeat measure within 48 hours of initial results
 - Treatment emergent serum creatinine > 180 µmol/L confirmed by repeat blood draw within 48 hours of initial results

Sponsor or PI can discontinue any subject at any time with or without DSC consultation. If such events (as described in #1, #2 above) occur and the subject is not discontinued from the study the reason for not discontinuing the subject will be included in DSC meeting minutes. Including, but not limited to the events listed above, the DSC may pause the study to additional dosing or dose escalation to provide time to evaluate safety data and recommend the action to be taken, which may include, but is not limited to one of the following:

- Discontinuation of a subject or group of subjects from the study
- The study is stopped immediately with no further dosing
- The study will continue until the current cohort is completed
- The study will continue, but the next dose escalation will be to a level midway between the current level and the next level specified in Section 8.3
- The study will continue as planned

If a serious adverse event (SAE) at least possibly related to study drug should occur for a single participant, subsequent dosing within that cohort **may** be put on hold pending a complete review of safety data by the DSC to determine if participant enrollment at the same dose may proceed, or if additional enrollment/dosing should stop. If following the DSC safety review it is deemed appropriate to restart dosing/enrollment, subject enrollment, dosing and dose escalation may proceed as planned.

6.4 *Duration of the Study*

For each NHV subject in the single dose cohorts, the duration of the study clinic visits is a maximum of 13 weeks from the beginning of the screening period to the Day 29 End-of-Study (EOS) examination.

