16 APPENDIX 1: ALT FLARE GUIDELINES

Fluctuations and elevations above ULN in ALT and AST are a normal part of CHB natural history. In fact, it is commonly believed that an elevation in ALT in the setting of undetectable or falling HBV-DNA, or in the setting of a decline in HBsAg may be a favorable prognosticator, representing immune system reconstitution against HBV. This is often referred to as an host induced flare. Similarly, elevated ALT in the setting of rising HBV-DNA may be a virus induced flare. In a first in human/first in patient clinical trial involving subjects infected with HBV, it is critically important to differentiate such causes of elevated ALT from drug induced liver injury which should inform the decision of whether to continue a subject with elevated ALT in the study. To facilitate this interpretation of ALT elevations the following guideline is provided.

Close monitoring and intercurrent diagnostic evaluations for any patient on study treatment (or placebo in blinded studies) who fits the following “ALT flare” definition:

- A rise in a patient’s serum ALT to a value that is > 3-fold above the patient’s Baseline ALT value (confirmed on repeat), and ALT value that is at least 10x ULN (confirmed on repeat)
- patient management should include a prompt clinic visit (and further follow-up visits when needed)
 - Drawn serum chemistry, hematology and cytokine Panel B and serially monitor if indicated. Immediately check and serially monitor albumin and direct bilirubin levels, to determine if liver functions are stable or deteriorating.
 - evaluate patient for potential causes of the ALT elevation, e.g.: intercurrent HAV, HEV, HCV or other infection; toxin exposures including acetaminophen, alcohol use, hepatotoxic herbal supplements or concomitant medicines.
 - patient’s recent HBV DNA levels should be checked for pattern of change. If HBV DNA is declining the ALT flare is presumptively not due to viral breakthrough (resistance) and could be a ‘beneficial’ (host immune system induced) flare if no intervening causes are found.

Study treatment interruption (pending diagnostic tests) or discontinuation for an ALT flare with biochemical evidence of hepatic decompensation should be considered as per protocol stopping rules.

PROTOCOL AMENDMENT SUMMARY OF CHANGES

PROTOCOL NUMBER: AROHBV1001

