### **10.3.2 Biostatistical methods**

All hematology, chemistry, coagulation and urinalysis parameters will be summarized using descriptive statistics for each dose level (cohort) for all time points assessed, including change from baseline (last pre-dose value) for all post-dose assessments. All continuous parameters will be summarized using the units reported from the laboratory.

Laboratory values will be compared to normal range of the single local laboratory and values that fall outside of the normal ranges will be flagged as: H (High) and L (Low) in the data listings. Results that were flagged as 'LP' will be reported as 'L' and results flagged as 'HP' will be reported 'H'. Shift tables from Day 1 (pre-dose) to all follow-up visits will also be generated for each hematology, chemistry and coagulation laboratory parameter with values of Within Normal Limits (WNL), High, and Low used for the shift categories.

To assess the liver function of CHB patients, number of subjects with ALT above the upper limit of normal over time will be summarized for CHB cohorts.

All laboratory data will be included in the by-subject data listings. Microscopic urinalysis will only be listed.

Time series of mean values for the following safety assessments will be plotted by NHV and CHB Cohorts.

- Creatinine
- Creatine Kinase
- AST
- ALT
- Total Bilirubin

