### **10.6.2 Biostatistical methods**

Descriptive statistics will be calculated for heart rate, PR interval, QRS interval, QT interval, and QTcF interval, including change from baseline (last pre-dose value on Day 1) for each dose level (cohort) for all time points assessed.

12-lead ECG measurements will be obtained at the scheduled time points after the participant is semi-supine for at least 3 minutes. Any abnormal ECGs will be repeated in triplicate, with each measurement approximately 1 minute apart. If triplicate ECG parameters are available, the average of the triplicate ECG parameters will be used. Unscheduled visits will be excluded from summary tables. However, the findings from the unscheduled will be listed.

In addition, the overall interpretation of 12-lead ECG results will be classified using frequency counts and percentages for the categories of Normal, Abnormal - Not Clinically Significant (NCS) and Abnormal - Clinically Significant (CS) for each treatment group for all time points assessed.

All ECG data will be presented in the by-subject data listings.

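### SAP 3 lets any safety laboratory repeat displace the original from the tables, so an abnormality that falls on a 48-hour confirmatory draw can be understated or lost there

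*SAP*

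**What the plan says.** SAP section 3 gives default rules that hold unless a later section departs from them. The default for repeated safety assessments is: "If there is a repeat test, the repeat result will be used in the analysis table and the original result will only be listed".

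SAP 10.3.2 does not depart from it for laboratory data. It plans descriptive statistics by time point. It adds shifts by visit ("Shift tables from Day 1 (pre-dose) to all follow-up visits will also be generated for each hematology, chemistry and coagulation laboratory parameter") for both populations, and an ALT count for CHB patients only ("number of subjects with ALT above the upper limit of normal over time will be summarized for CHB cohorts"). The table list in SAP 19 (14.3.4.1 to 14.3.4.8) matches this. The ECG section, SAP 10.6.2, does have its own rules: triplicates are averaged, and "Unscheduled visits will be excluded from summary tables". Laboratory data have no counterpart.

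The protocol's confirmatory draws follow abnormal results. Protocol 6.3 has stand-alone criteria for transaminases in healthy volunteers ("In NHVs, treatment emergent ALT or AST > 3X ULN which must be confirmed by repeat blood draw within 48 hours"), for platelets ("Treatment emergent platelet count < 70,000 per microliter in NHVs or < 50,000 in CHB patients, confirmed on repeat measure within 48 hours") and, in both populations, for creatinine. In CHB patients the transaminase criterion (above 3x baseline) must be met together with ALT above 10x ULN and either a bilirubin or an albumin change. Appendix 1 defines an ALT flare as a rise above 3-fold baseline "and ALT value that is at least 10x ULN (confirmed on repeat").

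On reporting, the protocol synopsis says: "The incidence of laboratory abnormalities will be assessed using descriptive summary statistics and shift tables".

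**The concern.** The protocol calls its confirmatory draw a repeat, and the SAP says a repeat replaces the original. Read together, a value abnormal enough to trigger confirmation is overwritten in the tables by the value that follows it. Because only abnormal values trigger these draws, the replacement is selective.

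The outputs exposed are the ones the protocol names for assessing laboratory abnormalities: descriptive statistics and shift tables. An unconfirmed abnormality that the investigator did not judge clinically significant, and that had no sequelae, would then appear only in a listing. The cohorts are small and safety is the primary objective, so a single such case is visible in the tables if kept and invisible if replaced.

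**Working it through.** **No plan figure to reproduce.** Neither document gives a repeat rate or a sample-size formula. The cohort sizes in SAP 2.4 and 2.5 do reconcile: CHB minimum 6×4 + 6×4 + 12 = 60, maximum 6×8 + 6×4 + 12 = 84; active healthy volunteers 5×4 = 20. One subject is 100/n percentage points: 25 (n=4), 12.5 (n=8), 8.3 (n=12), 5 (n=20).

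**Which outputs change, by reading of the SAP:**

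- Draw coded as unscheduled: the original stays at its visit and nothing changes.
- Draw coded as a repeat, lower but still out of range: the mean and extreme shrink; the High or Low category stays.
- Draw coded as a repeat, normal: the value also leaves the shift table and, for CHB ALT, the count above ULN.
- Draw coded as a repeat, more abnormal: the tabulated value becomes more extreme.

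Tables 14.3.4.1 to 14.3.4.8 contain no worst post-baseline summary and no count against the protocol thresholds, so none brings a displaced original back.

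**Average effect.** Healthy volunteers need screening ALT at or below ULN (protocol 7.2). Assumed model, in multiples of ULN: subject log-level = ln(m) + 0.30z; keep the subject if screening exp(level + s·z) ≤ 1; post-dose value = exp(level + s·z); 8,000,000 draws per setting. Post-dose values above 3x ULN, per million:

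| m | s = 0.15 | s = 0.20 | s = 0.30 |
|---|---|---|---|
| 0.5 | 0 | 0 | 2.1 |
| 0.7 | 0 | 0 | 48.1 |

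Random variation alone almost never triggers the rule. What is at stake is the recorded extreme in an individual case.

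**Illustrations (all values assumed).** Mean = ((n−1)·other + x)/n, where x is the subject's tabulated value.

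1. Healthy volunteer ALT, others 0.8x ULN, original 3.5x:

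| Tabulated x | Mean, n=4 | Change | Mean, n=20 | Change |
|---|---|---|---|---|
| 3.5 (original) | 1.475 | – | 0.935 | – |
| 2.5 | 1.225 | −16.9% | 0.885 | −5.3% |
| 0.9 | 0.825 | −44.1% | 0.805 | −13.9% |
| 4.5 | 1.725 | +16.9% | 0.985 | +5.3% |

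At 0.9x, one subject (1 of 4, or 1 of 20) leaves High. At 2.5x the category stays and the maximum falls from 3.5x to 2.5x.

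2. CHB ALT, others 0.8x, 11x replaced by 8x: n=4, 3.35 to 2.60 (−22.4%); n=8, 2.075 to 1.70 (−18.1%); n=12, 1.65 to 1.40 (−15.2%). The shift category and the count above ULN do not change, because 8x is still above ULN.

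3. CHB platelets (×10⁹/L), others 200, lower limit taken as 150, 45 replaced by 160: n=4, 161.3 to 190.0 (+17.8%); n=8, 180.6 to 195.0 (+8.0%); n=12, 187.1 to 196.7 (+5.1%). The minimum moves from 45 to 160 and one subject leaves Low (25, 12.5 or 8.3 points). A repeat of 100 would stay Low.

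**Direction.** A separate log-normal simulation assumed a between-subject CV of 50% and a trigger 1.3 between-subject SDs above the median on the log scale. For within-subject CVs of 10/20/30%, the repeat was below the first value in 60/68/74% of triggered cases, with a geometric mean ratio of 0.96/0.88/0.78. That trigger is about 1.85 times the median (exp(1.3 × 0.472)). The 3x ULN trigger is 4.3 to 6 times the median when the median is 0.7 to 0.5x ULN. The simulation therefore supports the direction of the effect, not its size.

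**The case against.** The strongest reply is that the loss depends on a coding choice not yet seen. A draw up to 48 hours later is a separate sample, and it could be recorded as unscheduled. Repeats in the SAP may have been meant for eligibility retests (protocol 9.3.6) or abnormal ECGs, and the CRO's operating procedures, to which SAP 3 refers, may define the term. The conditionality stands. But the SAP rule as worded covers any repeat, the protocol uses that same word for these draws, and unseen procedures cannot be relied on to override an explicit SAP rule. Tabulating both results is not an available reading either, since the rule sends the original to the listing only.

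Second, a value that is extreme and then normal within about 48 hours may be an invalid first sample, where replacement is right. That stands too, but the rule does not ask whether the first sample was invalid.

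Third, leaving the CHB count above ULN would need a fall from about 10x ULN to normal on a draw required by the CHB criteria, and no illustration shows it. That is fair: the category effect is more plausible for healthy volunteer transaminases and for platelets.

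Fourth, the rule is prespecified and also replaces values with worse repeats; all results stay in listings with H/L flags, which are readable at 4 to 12 subjects per cohort; and clinically significant abnormalities become adverse events. All true, and these facts limit the severity. They do not put the original back in the summary tables.

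Finally, neither document requires a worst-value table, so its absence alone is not an error. It matters here because it leaves no table that recovers a displaced value.

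**Conclusion.** The concern holds as a minor, conditional point. Applied as worded, the rule replaces abnormal laboratory values with their confirmatory results in the tables the protocol relies on for laboratory abnormalities. It does so only if those draws are treated as repeats, and it causes harm only where the original sample was valid.

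The size cannot be derived from the documents. The average effect is negligible: 0 to 48 chance triggers per million values in the healthy volunteer model. A single real case can matter within a cohort: under the assumed values, up to a 44% lower ALT mean and one of four subjects leaving High. Confirmed abnormalities that remain out of range keep their category. Listings, adverse event tables and stopping decisions are unaffected.

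**What to change.** Three changes to the SAP:

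- In section 3, keep the scheduled original in by-visit laboratory tables, and let a repeat replace it only when the original is documented as technically invalid.
- In 10.3.2, state that confirmatory draws are handled as unscheduled for laboratory data.
- Add one worst post-baseline laboratory table that includes repeat and unscheduled results, showing initial and confirmed counts side by side against the thresholds already in protocol 6.3.

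The cost is SAP wording, a record-selection flag and one table from data already collected. Counts may be slightly less favourable. The laboratory tables were part of the Day 113 interim set completed in February 2020 (SAP 17.2 and 19), so final Day 113 tables may differ from it; the clinical study report should say so, as SAP 16 already requires for changes to planned analyses.
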